Study participants who were randomized to the control group will have the opportunity to attend 6 weekly virtual diet information sessions after they complete final data collection visits and exit the study. Only participants whose schedules are compatible with course offerings by the dietitian will be able to attend. Diet information will align with national professional kidney organization recommendations. No research or monitoring data will be collected on participants who attend the 6-week session block. Invitations to participant in the post-study diet sessions will be mailed and/or emailed to former participants. Participants may also be contacted by phone by study staff and invited to participate.

Opportunity for participants who were screening for Cohort 5 during study cancellation:

We will provide an opportunity for study participants who were in the midst of screening for Cohort 5 to attend the diet counseling sessions that they otherwise would have received had we not ended the study. This will involve a one-on-one virtual diet session and 6 virtual diet group sessions led by the study dietitian, which is the same amount of access to the study dietitian that the control group was offered during the study. Participants will complete an in-center screening visit, per protocol, to confirm that it is safe to attend counseling sessions. Those who pass screening, thereby demonstrating that their blood pressure and labs meet original inclusion criteria, will be invited to participate in diet sessions only. Only participants whose schedules are compatible with course offerings by the dietitian will be able to attend. Diet information provided during the sessions will align with national professional kidney organization recommendations. Other than data collected during the screening visit, no research or monitoring data will be collected on participants who attend the 6-week session block. Because this activity is not a part of the research and does not involve an intervention, study participants will not be reconsented.

Selection of Subjects

Aim 1 Inclusion Criteria:

- Black race (self-identified)
- ≥ 21 years old
- CKD defined as an eGFR of 20-59 ml/min/1.73m²
- acknowledges self-awareness of CKD diagnosis
- Exclusion Criteria
- History of kidney transplant
- Lack of English language proficiency

Aim 2 Inclusion Criteria:

- Black race (self-identified)
- ≥ 21 years old
- CKD defined as an eGFR of 20-59 ml/min/1.73m²
- SBP ≥ 100 mm Hg

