- Stable kidney function

- Videoconference capabilities (access to mobile phone, laptop, desktop or tablet with working camera and internet connectivity)

Exclusion Criteria

- History of kidney transplant
- Receiving chronic dialysis
- Pregnant, lactating, or planning to become pregnant in 9 months
- Risk factors for hyperkalemia
- Screening serum potassium >5.0 mg/dl
- Screening serum bicarbonate <20 mg/dl
- History of hyperkalemia in the preceding 6 months defined as serum potassium greater than 5.0 mg/dl
- Use of oral potassium binders
- Dual therapy with an ACEI and an ARB
- Type 1 diabetes mellitus
- Type 2 diabetes with increased risk for glycemic event
- Hemoglobin A1C >10
- Hospitalization for glycemic event within the preceding 12 months
- If prescribed insulin or insulin secretagogue and unable to obtain permission from diabetes provider to participate in the study
- Change in anti-hypertensive medications within prior 4 weeks
- Hospitalization for hypertensive emergency in the preceding 6 months
- Hospitalization for psychiatric event in preceding 6 months
- Lack of English language proficiency
- Cardiovascular event within the preceding 12 months
- Excess alcohol use (>14 servings/week)
- Active malignancy other than prostate cancer and non-melanomatous skin cancer
- Inability to follow the study diet
- Special dietary requirements or restrictions other than vegetarianism (e.g., vegan)
- Resident of long-term care facility
- Household member of active study participant
- Participating in another clinical trial that will interfere with study activities or confound study outcomes

Subject Recruitment and Compensation

This study will use tools available in Maestro Care, such as DEDUCE (Duke Enterprise Data Unified Content Explorer) and Slicer/Dicer search tools, to help identify and recruit potential participants before consent is signed. We will also screen the schedules of clinics that are attended by our target population in high volume (e.g., nephrology, cardiology, hypertension clinic). Only key personnel who are delegated the task of patient identification/recruitment will have access to this information in Maestro Care. Prospective participants will be referred to the study by the following means:

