To evaluate preliminary efficacy of our counseling intervention on DASH adherence, BP, and potassium, we will repeat 24-hour diet recalls, 24-hour urine biomarker studies, office BP, 24-hour ABP, and clinical laboratory studies for all study participants at weeks 12 (post-intervention; primary endpoint) and 24 (after a 3-month post-study observation period; exploratory endpoint). We anticipate that active arm participants will exhibit greater improvement in DASH adherence and a larger reduction in 24-hour mean SBP. Initial summary statistics and graphical displays will be used to make reasonable outcome distribution assumptions. Using an intention to treat, primary analyses to compare the amount of change over time and trajectories of change between the two study arms in DASH diet score, 24-hour mean SBP, and serum potassium will use generalized linear mixed models, with a random effect to capture longitudinal within-person correlation. The primary model for BP outcomes will include study arm, time point, and their interactions, consistent with the randomized trial. Subsequently, a secondary model will be refit to adjust for age, gender, race baseline daily sodium intake, and time-specific values of eGFR, weight, and hypertension medication indicator. Exploratory outcomes in office SBP and DBP, 24-hour DBP, 24-hour urine biomarkers of diet adherence (potassium, phosphorus, urea, and sodium), and additional CKD-relevant metabolic markers (serum phosphorus and bicarbonate) will be assessed using the same analytic strategy. Our analytic approach can be used with any distribution within the exponential family (e.g., normal, binomial, Poisson, and skewed distributions such as gamma and lognormal). The decision on which is most appropriate will be made using initial summary statistics and graphs. The exponential family is broad enough that further transformations of the data are not expected to be necessary, but if so, we will use historically-common transformations to approximate normality. The proportion of participants who do and do not meet safety thresholds (serum potassium >5.2 mg/dl per testing lab standards, phosphorus >5.5 mg/dl, bicarbonate <18 mmol/L) in the two study arms will be compared using the same longitudinal generalized linear mixed model approach, assuming the Binomial distribution.

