Unlike a large clinical trial, our pilot study will not have statistical power to establish the effectiveness and safety of DASH in this population. However, this initial pilot study will generate critical evidence for estimating effect sizes and showing feasibility of the intervention, that will guide future work. Power:

Our power estimate is based on the primary aim comparing treatment arms on the SBP measure. Assuming a 20% attrition rate of 5 per group and using two-sided tests at a type I error rate of 5%, a final sample size of 20 per group will give us 80% power to detect a 7.7 mmHg difference in the change in SBP at 12 weeks between groups, assuming a within-person correlation of 0.7 over time and a standard deviation of SBP of 11 mmHg. A between-group difference of 11.4 and 7.8 mmHg were observed in prior DASH feeding and counseling intervention studies. To assess the sensitivity of the results to any missingness in the data, we will use multiple imputation to create complete cases while incorporating the uncertainty in doing so in the assessment of model parameters. The SAS/STAT software, version 15.1 for Windows and R packages (version 3.6.1) will be used for the data analyses, after extraction from the research database REDCap (Research Electronic Data Capture).

Phase 2c: For this qualitative aim, self-reported barriers and facilitators to DASH diet adherence among active arm participants will be described. Interview transcripts will be analyzed using framework analysis. A thematic analysis approach will be used to allow new concepts to emerge inductively from the data.

Data & Safety Monitoring

Safety monitoring:

Hyperkalemia: Hyperkalemia is the most serious potential risk that CKD patients who follow the DASH diet may experience. Therefore, we plan to actively monitor serum potassium concentrations during the intervention and intensify monitoring during periods that elevations in potassium, if they occur, would most likely be observed. When and how frequently we plan to measure serum potassium has been determined by:

- when participants will be counseled about potassium-rich and potassium-poor foods by the dietitian (i.e., week 2-3);
- knowledge about timing of steady-state concentrations of potassium following increased oral intake; and

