- lessons learned from our DASH diet pilot feeding study in which we observe trends in serum potassium among patients with CKD stages 3a and 3b who were given the DASH diet (i.e., Black adults with CKD). Participants in the feeding study had slightly lower risk for hyperkalemia due to their higher eGFR compared to the target population (CKD stages 3b and 4) being recruited for the current study.

As outlined in our proposal, serum potassium will be measured at the following scheduled intervals for participants who are randomized to the DASH diet counseling intervention: weeks 0, 2, 4, 8, and 12. Additionally, we plan to perform reflex laboratory testing contingent on the results from scheduled testing.

Blood pressure is a primary outcome for the study and will be measured during scheduled data collection visits. The study PI will be alerted during the study visit about participants with symptomatic severe hypertension or hypotension to make timely decisions about medical referral.

Hypoglycemia: Although DASH is not a low-carbohydrate diet, participants with Type 2 Diabetes Mellitus (T2DM) may be at risk for developing hypoglycemia if the carbohydrate content of DASH is lower than their typical daily consumption and they are prescribed insulin or insulin secretagogues. Safety oversight for study procedures involving patients with T2DM will be provided by [name], who is a Duke board-certified endocrinologist who specializes in caring for patients with diabetes. Investigators will take the following precautions to minimize risks of hypoglycemia and enhance the safe participation of patients with T2DM in the study:

Agreement of participants' diabetes provider (DP) to manage blood glucose (BG) Investigators do not assume responsibility for clinical care of the participants' diabetes. Potential participants with T2DM who are prescribed insulin or an insulin secretagogue will only be allowed to participate in the study if their DP (i.e., primary care provider or endocrinology provider) approves of their participation and agrees to manage their diabetes medications during the study (see "Diabetes Provider Opt-in Contact Protocol"). Participants will be advised to maintain follow up appointments with their DP and to seek sooner follow-up if indicated for abnormal glucose values.

Blood glucose self-monitoring

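### Serum potassium limits (entry and safety) and the bicarbonate entry limit are printed in mg/dl, but the numbers make sense only in mmol/L

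*Combined protocol and SAP*

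**What the plan says.** Under Selection of Subjects, the Aim 2 exclusion criteria contain three laboratory limits that matter here:

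- The potassium limit at the screening visit reads "Screening serum potassium >5.0 mg/dl".
- The bicarbonate limit at the same visit reads "Screening serum bicarbonate <20 mg/dl".
- The criterion on past potassium results reads "History of hyperkalemia in the preceding 6 months defined as serum potassium greater than 5.0 mg/dl".

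Under Phase 2b analytic strategy, the safety thresholds are "serum potassium >5.2 mg/dl per testing lab standards, phosphorus >5.5 mg/dl, bicarbonate <18 mmol/L". The proportions beyond these thresholds are to be compared between arms with a longitudinal binomial mixed model.

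Data & Safety Monitoring states that "Hyperkalemia is the most serious potential risk that CKD patients who follow the DASH diet may experience". It gives a schedule of potassium measurements and adds that "we plan to perform reflex laboratory testing contingent on the results from scheduled testing", with no numeric trigger.

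The section on people who were screening for Cohort 5 when the study was cancelled still requires a screening visit. Those who pass are described as "thereby demonstrating that their blood pressure and labs meet original inclusion criteria".

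**The concern.** Four limits carry a unit that does not fit their numbers: potassium twice at entry and once for safety, and bicarbonate once at entry. Bicarbonate is also inconsistent within the plan, in mg/dl at entry and in mmol/L for safety.

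These are decision limits, not background text. The three potassium figures are the only numeric serum potassium limits in the document, so no other section supplies a correct one. The Risk/Benefit Assessment relies on excluding people with raised potassium at baseline to limit electrolyte risk, and the Aim 2 hypothesis is that blood pressure falls without hyperkalemia.

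Two uses outlast the end of recruitment. The 5.2 threshold defines a safety proportion to be reported by arm, and the original laboratory criteria serve as a safety gate for the Cohort 5 screenees. (That section speaks of inclusion criteria while the potassium and bicarbonate limits sit under exclusion. Its stated safety purpose makes them the natural reference.)

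**Working it through.** The plan derives none of these limits, so there is no figure of its own to reproduce. The check is a unit conversion.

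**Inputs from the document**

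- Potassium, entry (screening and history): 5.0 mg/dl (Aim 2 Exclusion Criteria)
- Bicarbonate, entry: 20 mg/dl (Aim 2 Exclusion Criteria)
- Potassium, safety: 5.2 mg/dl (Phase 2b analytic strategy)
- Bicarbonate, safety: 18 mmol/L (Phase 2b analytic strategy)

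**Physical constants, not in the document:** molar mass 39.098 g/mol for potassium and 61.017 g/mol for bicarbonate. Both ions are monovalent, so mmol/L equals mEq/L.

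**Formulas:** mmol/L = mg/dl × 10 / molar mass; mg/dl = mmol/L × molar mass / 10.

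| Limit | As printed, converted to mmol/L | Same number in mmol/L, converted to mg/dl | Factor |
|---|---|---|---|
| Potassium 5.0 | 5.0 × 10 / 39.098 = 1.28 | 5.0 × 3.9098 = 19.5 | 3.9 |
| Potassium 5.2 | 5.2 × 10 / 39.098 = 1.33 | 5.2 × 3.9098 = 20.3 | 3.9 |
| Bicarbonate 20 | 20 × 10 / 61.017 = 3.28 | 20 × 6.1017 = 122.0 | 6.1 |

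**Internal check on bicarbonate.** This needs only the plan's two limits and the molar mass. The literal entry limit is 3.28 mmol/L and the safety limit is 18 mmol/L (18 × 6.1017 = 109.8 mg/dl). The ratio is 18 / 3.278 = 5.5. Anyone between 3.28 and 18 mmol/L could enroll while already beyond the safety threshold. With entry at 20 mmol/L the order is sensible: the entry limit is stricter than the safety limit.

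**Potassium.** Assume, for illustration, that serum potassium runs from 3.5 to 5.0 mmol/L. That is 3.5 × 3.9098 = 13.7 to 19.5 mg/dl. The lowest of these values is 13.7 / 5.0 = 2.7 times the printed entry limit, so the conclusion does not depend on the exact range. Literally applied, the exclusion removes everyone. The safety flag is positive for everyone at every visit in both arms, so the binomial model has no variation to analyze.

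**Bicarbonate exclusion.** On an assumed range of 15 to 30 mmol/L (91.5 to 183.1 mg/dl), every value is far above 20 mg/dl, so the criterion as printed removes nobody.

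**What is not affected.** Phosphorus above 5.5 mg/dl and bicarbonate below 18 mmol/L are usable as printed. The gaps between entry and safety limits (5.0 against 5.2, 20 against 18) are not errors. The power statement rests on systolic blood pressure inputs and uses none of these limits.

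**The case against.** The strongest reply is that the literal reading cannot have been used at entry. The document describes earlier cohorts and a control group that was offered sessions, so people were enrolled, whereas a literal potassium limit would have excluded them all. That stands, and it means staff almost certainly read mmol/L at screening.

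Second, the potassium safety limit is tied to the laboratory: "serum potassium >5.2 mg/dl per testing lab standards". All biospecimens go to one certified laboratory. This supports the number 5.2 and makes misapplication less likely. It does not supply a correct unit, because the document does not state the laboratory's reporting unit.

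Third, participant protection does not hang on the printed figure alone. Action on abnormal results is dietary counseling, or withdrawal at the investigator's discretion, and reflex-testing limits may be set out in the separate proposal to which the monitoring section refers. This too is fair and limits the likely harm.

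Fourth, the statistical reach is small. Potassium is also compared as a continuous outcome, which needs no cut-off, and the plan says the pilot is not powered to establish safety. Nothing has been miscalculated; the fault is a unit label. No analysis code is available, so an actual coding error is a possibility and has not been shown.

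These points bear on weight. None makes the printed limits correct. The safety sentence also mixes correct and incorrect units, with mg/dl right for phosphorus and wrong for potassium, which makes copying the wrong one easier.

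**Conclusion.** The concern holds, with high confidence. The wrong unit recurs in clean text in two separate sections, so a PDF-reading fault is unlikely, and nothing elsewhere in the document corrects it.

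The bicarbonate inconsistency is visible in the document itself. The potassium error rests on molar mass and on the assumption that living participants' serum potassium lies well above 1.33 mmol/L. That staff worked in mmol/L is an inference and is not stated in the plan.

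The practical effect is probably small and no estimate of power or sample size changes. Because these are eligibility and safety limits in a trial whose chief hazard is hyperkalemia, they should be corrected.

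**What to change.** In the Aim 2 exclusion criteria, change the unit to mmol/L for both potassium limits (above 5.0, at screening and in the six-month history) and for the bicarbonate limit (below 20). In the Phase 2b analytic strategy, change the unit of the potassium safety threshold (above 5.2) to mmol/L and keep the reference to the testing laboratory's standards. Leave the phosphorus threshold and the bicarbonate safety threshold as they are.

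Before the safety proportions are run, confirm that the analysis code applies 5.2 to potassium values held in mmol/L, and that tables and reports carry the corrected unit.

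The cost is four unit corrections and one check of the code. No new data, visits or analyses are needed.

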During the second phase (Aim 2) fifty participants will be recruited, enrolled and randomized 1:1 to either the Standard of Care (Control) Group or the Intervention Group. Participants in both groups will be compensated up to a total of \$250 for travel, lost wages, and time. ClinCards will be given to each participant and payments for each of the 4 data collection visits will be uploaded after the assessments that are assigned to each respective visit are completed. They will receive: \$50 for completing all baseline assessments, \$50 for completing all 4 week assessments, \$100 for completing all 12 week assessments, and \$50 for completing all 24 week assessments. Payments will be prorated for completing questionnaires, biospecimens, BP measurements, and dietary recalls at each visit.

Participants who consent for Aim 2 will have the option of sharing their experiences and thoughts about participating in research with the Duke Research Equity and Diversity Initiative (READI) project. The READI project aims to better understand and improve participants' experiences in research studies.

Participants will indicate on the consent form whether they agree to share their contact information (name and email address) with the READI project, or not. If they do, they will be invited to share the information on their experience through surveys.

Participants enrolled and randomized in Aim 2 will have the option to choose to have additional blood samples collected and stored for future research. This option requires participants to sign a separate consent form that provides details about the storage and potential future use. The additional sample will be collected at the same time other blood draws are conducted for the main study. No additional visit or venipuncture will be required and no additional compensation will be provided for the optional collection.

Risk/Benefit Assessment

Potential risks: (Phase 2 participants only)

- Electrolyte abnormalities
- Hyperkalemia: the DASH diet is rich in potassium. Urinary excretion of potassium is diminished as kidney function worsens. If severe, hyperkalemia can result in muscle weakness and paralysis, cardiac conduction abnormalities, cardiac arrhythmias, metabolic acidosis and death.

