We anticipate that participants will be accrued within a 18 month period at a rate of 3 participants per month. To determine the feasibility of conducting our intervention in a larger randomized controlled trial, we will evaluate rates of study enrollment, group attendance, completed data collection, and study retention. We will also assess reasons for study refusal and withdrawal. We will consider the study feasible if we are able to recruit 50 participants in 18 months. To determine acceptability, we will ask participants how useful the intervention was (1="Not at all useful" to 5="Extremely useful"), whether the intervention will change their diet (1="Will not change at all" to 5="Will change a lot"), and whether they would recommend the program to a friend (1="Definitely would not recommend" to 5="Definitely would recommend"). For the intervention to be deemed acceptable, 75% of participants in the intervention group would have to rate each item a "4" or a "5."

Phase 2b analytic strategy

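### The feasibility rule uses recruitment alone, so the pilot would be declared feasible at any level of dropout, although its design assumes 20% attrition

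*Combined protocol and SAP*

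**What the plan says.** Under Data Analysis & Statistical Considerations, the Phase 2a analytic strategy gives its purpose as "To determine the feasibility of conducting our intervention in a larger randomized controlled trial". For that purpose "we will evaluate rates of study enrollment, group attendance, completed data collection, and study retention", and reasons for refusal and withdrawal will also be assessed. One criterion follows: "We will consider the study feasible if we are able to recruit 50 participants in 18 months". No threshold is attached to attendance, data completion or retention. A separate rule covers acceptability: 75% of the intervention arm must give one of the top two ratings on each of three items.

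Under Subject Recruitment and Compensation, "fifty participants will be recruited, enrolled and randomized 1:1", which is 25 per arm. The power paragraph in the Phase 2b analytic strategy starts from "Assuming a 20% attrition rate of 5 per group" and bases 80% power for a 7.7 mmHg difference in SBP change at 12 weeks on 20 per group. It also says that the pilot is not powered to establish effectiveness and safety, and that its role is to estimate effect sizes and show feasibility.

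**The concern.** Four measures are collected to answer one question, and the stated rule lets only the first decide it. Recruiting 50 people in 18 months shows that patients will join. It does not show that they stay through 12 weekly group sessions, or that they return for 24-hour ambulatory monitoring at week 12.

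Feasibility is one of the pilot's two declared products, and the more important one because power for effectiveness is disclaimed. A rule that ignores dropout can recommend a larger trial of a design that loses far more participants than planned. It also cannot detect unequal loss, which is plausible here: the intervention arm has 12 group sessions of about 60 to 90 minutes on top of the single session that both arms receive. The acceptability rule does not close the gap. It rests on ratings by intervention participants and sets no limit on dropout in either arm.

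**Working it through.** **1. What the rule depends on.** Its inputs are the number recruited and the elapsed time. With 50 recruited in 18 months the result is feasible for every retention value from 0 to 50.

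**2. The plan's own figure, reproduced.** Inputs from the power paragraph: SD 11 mmHg, within-person correlation 0.7, difference 7.7 mmHg, two-sided 5%, 20 per group.
- SD of change = 11 × √(2 × (1 − 0.7)) = 8.52 mmHg.
- Standard error = 8.52 × √(2/20) = 2.694, and 7.7 / 2.694 = 2.858.
- Power = 81.5% (normal approximation) or 79.5% (noncentral t, 38 df). The detectable difference at 80% power is 7.55 or 7.75 mmHg. The stated 80% and 7.7 mmHg are reproduced.
- 20 / (1 − 0.20) = 25 per arm, or 50 in total. The number to be recruited was therefore obtained by assuming 80% retention.

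**3. Illustration at higher loss.** The loss rates are hypothetical, only week-12 completers are counted, and the noncentral t is used.
- 15 per arm (40% lost): standard error 3.111, ratio 2.475, power 66.6%, detectable difference 9.0 mmHg.
- 12 and 13 (half lost): standard error 8.52 × √(1/12 + 1/13) = 3.411, ratio 2.257, power 58.0%, detectable difference 10.0 mmHg.

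Both detectable differences exceed 7.8 mmHg, the smaller of the two prior effects that the plan cites. The feasibility verdict is the same in both cases.

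**4. How a retention criterion would behave.**
- A hard pooled cut of at least 40 of 50 is met with probability 7.9%, 58.4%, 88.0% and 99.1% if true retention is 70%, 80%, 85% and 90% (binomial, n = 50). At exactly 80% it fails 100 − 58.4 = 41.6% of the time. It would also pass 25 in one arm and 15 in the other.
- An observed 40 of 50 has an exact 95% interval of 66% to 90%.
- By arm, with not feasible declared if the exact upper 95% limit is below 80%: 15 of 25 has interval 38.7% to 78.9% and fails; 16 of 25 has 42.5% to 82.0% and passes. The rule therefore fails an arm at 15 or fewer.
- The chance that a given arm fails is P(X ≤ 15), X binomial with n = 25: 1.7% at true retention 80%, 18.9% at 70%, 57.5% at 60% and 88.5% at 50%. The chance that at least one of two independent arms fails is 1 − (1 − p)²: 3.4%, 34.3%, 82.0% and 98.7%.

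**The case against.** The strongest reply is that retention is not ignored. It is listed, it will be reported with reasons for withdrawal, and any reader would notice heavy dropout. Whether a pilot needs a pass mark for every measure is partly preference. That stands as far as it goes: a reader might infer that the plan overlooks retention, and it does not. But the plan chose to state a success criterion, and that criterion disregards three of the four measures named for the purpose.

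A second reply is that 20% attrition is a planning input for this pilot's SBP comparison, not a feasibility standard. A larger trial could enlarge its sample to cover whatever loss is seen here. This also stands. A reader might infer that power needs 80% retention, or that heavier loss would leave the pilot unable to deliver its primary endpoint. The documents support neither. Power declines gradually, about 30 week-12 outcomes would remain at 40% loss, and the mixed model uses partial follow-up, with multiple imputation as a sensitivity analysis. These methods may recover some information, but they do not show that participants can be retained.

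A third reply concerns timing. Under Design & Procedures, the paragraph on participants screening for Cohort 5 shows that the study was ended during that screening. The documents give neither the number randomized nor any observed dropout, so it is unknown whether 50 were recruited or how many were lost. This affects how an added criterion must be labelled; the rule is deficient either way.

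**Conclusion.** The point holds in a limited form. The stated rule can return feasible at any level of dropout, and the plan supplies a benchmark, 80% retention at week 12, that the rule does not use. This follows from the text and needs no calculation. The damage is to the go/no-go conclusion for the larger trial.

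The power figures (about 67% at 15 per arm, 58% at 12 and 13) only illustrate the cost. They rest on the plan's SD and correlation, on hypothetical loss rates and on completers alone, in a pilot that disclaims power for effectiveness. They do not show that a larger trial would be infeasible. The 80% benchmark is the plan's assumption, and the sponsor may justify another value. The point should be addressed; it does not invalidate the design.

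**What to change.** Replace the single criterion with two. Declare feasibility only if 50 participants are recruited in 18 months and week-12 retention is compatible with the assumed 80%. Judge retention by arm, with randomized participants as the denominator and exact 95% confidence intervals; for example, not feasible if the upper limit in either arm is below 80%. Report completion of week-12 24-hour SBP by arm alongside it, kept separate because a retained participant may still lack a usable recording. State how participants withdrawn by the investigators are counted.

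The interval rule is lenient: it passes 16 of 25, and at true retention of 70% it stops the trial only about a third of the time. If the sponsor prefers a hard cut such as 40 of 50, the plan should acknowledge that it fails about 42% of the time when true retention is exactly 80%, and that a pooled count can hide imbalance between arms.

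The edit is short and needs no new data collection. Its cost is a feasibility bar that is harder to pass. If retention data have already been seen, the criterion must be labelled as added later, with the 20% attrition assumption cited as its source.
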